2.6.1.1 Use of lenses

Both lens types will be worn in the clinic only.

2.6.2 Care regimen

No care system will be used on this study.

2.6.3 Inventory control

Both Proclear Multifocal Toric and Biofinity Toric Multifocal lenses will be supplied by CooperVision Inc.

Lenses of interest such as those with device deficiencies will be stored and reported to the Sponsor. If the lens is likely to have caused or contributed to a serious adverse event, this will be reported as soon as possible.

Lenses which have been stored during the study, will be discarded on completion of the study report, unless advised otherwise by the Sponsor. All study lenses will be destroyed at the end of the study.

There will be an accurate accounting of the study test product at the completion of the study.

All used study test products will be documented (Lot number; Expiry date etc.) in the study CRF.

2.6.4 Clinical equipment

Clinical equipment is regularly maintained and calibrated as required. Standard operating procedures and international standards are used where appropriate.

2.7 Study control

This study is controlled by cross-comparison. Subjects will be masked to the two lens types by means of the investigator opening the lens packaging and ensuring that the subject does not see the lens foil details. Masking may be 'broken' if deemed necessary, by the Principal Investigator or Sponsor.

2.8 Documentation

Documents related to this work that require archiving will be kept by Eurolens Research for a period of 20 years after completion of the final report. The Sponsor's permission will be sought before the documents are destroyed.

2.9 Data collection and analysis

Data collected in this work will be recorded on a custom-developed database and an established data trail. Data handling will include export of the study information from the clinical database into spreadsheet format for manipulation, followed by export into a statistical package for analysis. Most clinical data will be entered directly onto the electronic case report form and are considered to be source data.

2.10 Study completion

The clinical phase of the study will be considered as complete when all subjects have attended their last visit.

2.11 Subject confidentiality

All matters related to this work will remain confidential within Eurolens Research, the Sponsor and any regulatory authority (e.g. Manchester UREC). Eurolens Research will take all reasonable steps to ensure that specific lens-related information is not passed on to study subjects unless this is required for clinical management of an adverse event. Personal subject information will not be made available. To cater for this, subjects will only be referred by their unique identity number in the study report. The data activities of Eurolens Research are registered with the data protection officer at The University of Manchester.

2.12 Study monitoring

In order to provide quality control and quality assurance as part of this work, the study monitor will:

1. Liaise closely with the Principal Investigator.
2. Monitor and ensure the safety of the subjects.
3. Ensure that the investigation is being conducted according to the protocol.
4. Monitor and review (or oversee review of) the study records to ensure accuracy.
5. Review study product accountability.
6. Document their observations and make them available to relevant authorised parties (e.g. Manchester UREC).
7. Implement the Eurolens Research clinical monitoring standard operating procedure.

Section 3. Subject management

3.1 Visit scheduling

Subjects will be required to attend two visits. Visit 1 will determine the ideal contact lens specifications, and visit 2 will assess both lens types. Subjects may wear their habitual contact lenses and/or spectacles between the two visits.

Visit	Target	Allowable range
Visit 1	N/A	N/A
Visit 2	N/A	N/A

Table 3: Visits and allowable ranges.

3.1.1 Repeat visit 1

Should a subject attend visit 1 and be ineligible for the study owing to a reason which the investigator believes to be transient

a repeat first visit can be conducted a short time later. This visit may involve some or all of the scheduled initial visit procedures, with the exception of the consent process, which would not be repeated.

3.1.2 Unscheduled visits

An unscheduled visit is an interim visit requested by the subject or investigator due to an unanticipated event.

3.1.3 Missed visits

Subjects not attending for a visit will be contacted and encouraged to return for assessment. If two consecutive study visits are missed, the subject will be discontinued. It is expected that Eurolens Research personnel will attempt all reasonable means of communication in this event, including corresponding with the subject by letter.

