2.1.1 Subject withdrawal and replacement

This study includes two clinical visits. Once the study consent form is signed, the subject is considered to be enrolled on the study. Subjects who have signed the consent form, but who have not completed the initial visit will usually be replaced. All subject data will be included in the final analyses unless there are strong grounds for exclusion; such grounds will be detailed in the final report.

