In general, subjects should be discontinued at any time, if it is in their best interests, as judged by the investigator. Reasons for this may include clinical signs of grade 3 or more, lack of motivation, discomfort, repeated refusal to follow instructions or the use of non-study products such as solutions or lenses. Subjects will be discontinued if a serious adverse event occurs or if they miss two or more planned consecutive visits. Subjects who fail to satisfy all the inclusion and exclusion criteria will be discontinued and replaced. Subjects who choose to leave the study at their own request will be replaced. All discontinuations will be carefully recorded.

2.3 **Safety parameters, adverse events and concurrent illnesses**

The key safety parameters are the serious and significant ocular adverse events listed in

Clinical assessment is made at the study visit(s) for these parameters. The presence of an adverse event will be reported on the case report forms and those described as 'serious' or 'significant' will be detailed in the final report. Similarly, any concurrent illness that is likely to impact on the relevance and quality of the captured data will be noted on the case report form.

2.3.1 **Investigator responsibilities**

The investigator will be appropriately qualified, have suitable resources to conduct the study, have study training, ensure subject safety and data integrity. At all times they will act in the best interest of the subject. Referral or treatment of an adverse event or other clinical finding should be initiated in the best clinical judgement of the investigator, irrespective of their participation in the clinical study.

2.3.2 **Investigator reporting responsibilities**

In the case of a 'serious' or 'significant' adverse event, the Principal Investigator will notify the Sponsor as soon as possible. Manchester UREC and any regulatory authorities will be informed as required.

2.4 **Study termination**

If it becomes necessary to terminate the study earlier than planned, the Sponsor will notify the Principal Investigator who will end the study with the cooperation of other staff members. Manchester UREC will be informed.

2.5 **Protocol deviations**

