3.2.2 Informed consent

The subject will be required to sign an informed consent form prior to enrolment (Appendix B) and before any procedures specific to the clinical investigation are performed. A copy of the signed form will be issued to the subject. When the subject has signed the consent form, they are considered to be enrolled on the study.

3.2.3 Visit 1

Subjects should attend wearing their spectacles.

Written consent from the subject will be obtained as detailed in section 3.2.2.

Subjects will be instructed on the following:

1. [REDACTED].
2. Specific study instructions, such as the importance of not using any other contact lens products.
3. General contact lens information such as the management of red eyes.

The following procedures will be performed (any ocular measurement procedures outlined below will be carried out on each eye):

1. Details of the ocular, medical and contact lens-wearing histories of the subject will be noted [REDACTED]
2. [REDACTED].
3. [REDACTED]
4. [REDACTED]
5. [REDACTED]

[REDACTED]

[REDACTED]

[REDACTED]

[REDACTED]

[REDACTED]

[REDACTED]

The presence of any adverse events will be recorded [REDACTED]

6. The investigator will confirm that the subject satisfies all the inclusion and exclusion criteria. Subjects who fail to meet all the criteria at this time will usually be discontinued and replaced. If the investigator deems the ineligibility to be transient (section 3.1.1), this initial visit may be repeated.
7. Using the fitting set, the Proclear Multifocal Toric lens will be applied and allowed to settle for 15 minutes. The closest available lens specification to the subject's prescription will be selected.
8. [REDACTED]
9. The Proclear Multifocal Toric lenses will be removed.
10. Using the fitting set, the Biofinity Toric Multifocal lenses will be applied and allowed to settle for 15 minutes. The closest available lens specification to the subject's prescription will be selected.
11. [REDACTED]
12. The Biofinity Toric Multifocal lenses will be removed.
13. [REDACTED]
14. [REDACTED]
15. The study lenses will be ordered, taking into account the manufacturers fitting guide [REDACTED]
16. The subject will then be notified of expected timelines for lens receipt and will be subsequently contacted to arrange visit 2. Subjects may wear their habitual lenses and/or spectacles between the two visits.

3.2.4 Visit 2

1. Any changes to ocular or general health and medication will be recorded.

2. [REDACTED]

[REDACTED]

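### Do the missed-visit, replacement and habitual-lens rules, which fit a two-visit study poorly, put the paired data at risk?

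*Combined protocol and SAP*

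**What the plan says.** All references are to the combined protocol and SAP.

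- **Visits.** Section 3.1: "Subjects will be required to attend two visits". Visit 1 sets the lens specifications and visit 2 assesses both lenses. Consent is signed at visit 1 and marks enrolment (sections 3.2.2 and 3.2.3). Table 3 marks the target and range of both visits as not applicable.
- **Missed visits.** Section 3.1.3: "If two consecutive study visits are missed, the subject will be discontinued". Section 2.2 agrees: "Subjects will be discontinued if a serious adverse event occurs or if they miss two or more planned consecutive visits". After a single missed visit, staff contact the subject and encourage attendance.
- **Replacement.** Section 2.1.1 covers consented subjects "who have not completed the initial visit will usually be replaced". Section 2.2 adds ineligible subjects and those who leave by their own choice.
- **Other lenses.** Section 3.1: "Subjects may wear their habitual contact lenses and/or spectacles between the two visits". Section 3.2.3 has subjects instructed on "the importance of not using any other contact lens products". Section 2.2 lists "the use of non-study products such as solutions or lenses" among possible reasons for discontinuation.
- **End of study.** Section 2.10 treats the clinical phase as "complete when all subjects have attended their last visit".
- **Sample size.** Section 1.5.2 requires 30 subjects for power of at least 0.80 on four scores, and recruits up to 40.

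**The concern.** An enrolled subject normally has only visit 2 left to miss, so a rule that needs two consecutive misses hardly ever operates. In the visible schedule the primary outcome, subjective distance vision, is scored only at visit 2. A subject who stays away therefore gives no pair, and neither replacement passage names that case. Read literally, such a subject would be neither discontinued nor replaced, and the completion condition in section 2.10 would stay open.

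Separately, study lenses are worn only in the clinic (section 2.6.1.1), so any lens worn between visits is a non-study lens. A subject who uses the permission in section 3.1 then meets a listed discontinuation reason. Inclusion criterion 5 requires current or recent soft lens wear, so this could touch many subjects.

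At stake would be the number of complete pairs on which the power rests, and consistent handling of subjects who wear their habitual lenses.

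**Working it through.** **1. Missed visits.** The two-visit threshold appears in both sections 2.2 and 3.1.3, against a schedule with one visit left after enrolment. The remaining route is narrow: a repeat visit 1 (section 3.1.1) missed after consent, followed by a missed visit 2. The rule does not fit, but it is not the only provision. Section 2.2 lets the investigator discontinue at any time in the subject's interest and gives poor motivation as one example.

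**2. Replacement.** The claim that no-shows are not replaced is read from silence. Section 2.1.1 says who is usually replaced; it does not limit replacement to them. A persistent non-attender could be treated as having chosen to leave, which section 2.2 replaces. Sections 1.5.2 and 2.1 already provide for losses by consenting up to 40 to complete 30.

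**3. The plan's own figure.** Inputs from section 1.5.2: margin 10, alpha 0.05, power 0.80, SDs 18 (comfort), 16 (distance), 19 (near), 17 (overall). Assumptions: true difference zero, and each SD is that of the paired difference. For two one-sided tests, normal approximation:

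n = SD² × (1.645 + 1.282)² / 10² ≈ SD² × 0.0856

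This gives 22 (distance), 25 (overall), 28 (comfort) and 31 (near). The largest is one above the stated 30, so the figure is reproduced closely. The exact t version needs 24, 27, 30 and 33.

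**4. Effect of lost pairs (exact t version).**

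| Score | SD | Power, 30 pairs | Power, 27 pairs | Drop |
|---|---|---|---|---|
| Distance (primary) | 16 | 0.910 | 0.871 | 0.039 |
| Overall | 17 | 0.867 | 0.817 | 0.050 |
| Comfort | 18 | 0.815 | 0.756 | 0.059 |
| Near | 19 | 0.758 | 0.691 | 0.067 |

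With all 40 consented, 27 pairs means 40 − 27 = 13 losses, or 13/40 = 32.5%. Distance vision keeps power of at least 0.80 down to 24 pairs (0.815), which is 16 losses, or 16/40 = 40%.

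The documents give no loss rate. Under assumed rates with 40 consented:

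| Assumed loss | Chance of at least 30 completers |
|---|---|
| 10% | 0.999 |
| 15% | 0.970 |
| 20% | 0.839 |
| 25% | 0.584 |
| 30% | 0.309 |

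Even at 30%, the expected number is 40 × 0.70 = 28 pairs, at which distance-vision power is 0.885.

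**5. Bias.** A subject absent from visit 2 has neither lens score, so the pair is lost whole and neither lens is favoured by half-observed pairs. Habitual wear between visits precedes both lenses, which are scored at the same visit, so it is common to both sides of the comparison.

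**6. Habitual lenses.** Sections 3.1 and 3.2.3 (item 16) give the permission; the instruction in section 3.2.3 and the ground in section 2.2 point the other way. This is a real contradiction. The ground is one of several possible reasons left to the investigator's judgement, so it removes nobody automatically. Part of the visit 1 instruction list is redacted, so its full content cannot be seen.

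**7. Completion and window.** Section 2.10 refers to each subject's last visit, not to visit 2, and section 3.2.4 (item 20) allows for subjects whose participation ends earlier. The not-applicable entry in Table 3 is explicit. Lenses are ordered after visit 1, visit 2 is arranged later, and no dispensed wear period has to be timed.

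**The case for a change.** The strongest case for a change is that the text fails exactly where the primary data are collected. Visit 2 is booked after an open-ended wait for ordered lenses, so non-attendance is plausible, and no sentence says what then happens. The plan claims 0.80 for four scores, yet three lost pairs take comfort from 0.815 to 0.756. A few sentences would settle it at no cost in visits or subjects.

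Part of this stands. The missed-visit wording does not suit the design, and the habitual-lens passages contradict each other. Comfort would fall below 0.80 at 27 pairs, but with full recruitment that takes 13 losses. Near vision is below 0.80 even at 30 pairs, so these rules are not the cause.

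The proposed replacement rule would work within the same ceiling of 40, so the maximum enrolment is unchanged. A visit window would add detail without altering the comparison.

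**Conclusion.** No change to design, sample size or analysis follows. What remains is a wording inconsistency of low severity, probably text carried over from longer studies. The passages on missed visits, and those on habitual and non-study lenses, must be reconciled; which rule should apply is not a statistical question. No estimate, stated figure or conclusion depends on it.

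The 40-for-30 allowance covers 25% loss, and primary-outcome power holds at 0.80 or more down to 24 pairs. Sections 1.5.1 and 2.2 have the number in each analysis reported and every discontinuation recorded, so any shortfall would be visible.

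The power figures assume a true difference of zero and that the SDs in section 1.5.2 are those of paired differences. If they are within-subject SDs instead, they grow by √2 and the normal approximation needs 44 to 62 subjects. The lowest of these already exceeds the ceiling of 40, so no replacement rule within that ceiling would help. That question belongs to the power section, not to these rules.

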3.2 Visit conduct

3.2.1 Pre-enrolment

The subject will receive a study-specific information form outlining the study at least 24 hours before giving written consent.

3.2.2 Informed consent

The subject will be required to sign an informed consent form prior to enrolment (Appendix B) and before any procedures specific to the clinical investigation are performed. A copy of the signed form will be issued to the subject. When the subject has signed the consent form, they are considered to be enrolled on the study.

3.2.3 Visit 1

Subjects should attend wearing their spectacles.

Written consent from the subject will be obtained as detailed in section 3.2.2.

Subjects will be instructed on the following:

1. [REDACTED].
2. Specific study instructions, such as the importance of not using any other contact lens products.
3. General contact lens information such as the management of red eyes.

The following procedures will be performed (any ocular measurement procedures outlined below will be carried out on each eye):

1. Details of the ocular, medical and contact lens-wearing histories of the subject will be noted [REDACTED]
2. [REDACTED].
3. [REDACTED]
4. [REDACTED]
5. [REDACTED]

[REDACTED]

[REDACTED]

[REDACTED]

[REDACTED]

[REDACTED]

[REDACTED]

The presence of any adverse events will be recorded [REDACTED]

6. The investigator will confirm that the subject satisfies all the inclusion and exclusion criteria. Subjects who fail to meet all the criteria at this time will usually be discontinued and replaced. If the investigator deems the ineligibility to be transient (section 3.1.1), this initial visit may be repeated.
7. Using the fitting set, the Proclear Multifocal Toric lens will be applied and allowed to settle for 15 minutes. The closest available lens specification to the subject's prescription will be selected.
8. [REDACTED]
9. The Proclear Multifocal Toric lenses will be removed.
10. Using the fitting set, the Biofinity Toric Multifocal lenses will be applied and allowed to settle for 15 minutes. The closest available lens specification to the subject's prescription will be selected.
11. [REDACTED]
12. The Biofinity Toric Multifocal lenses will be removed.
13. [REDACTED]
14. [REDACTED]
15. The study lenses will be ordered, taking into account the manufacturers fitting guide [REDACTED]
16. The subject will then be notified of expected timelines for lens receipt and will be subsequently contacted to arrange visit 2. Subjects may wear their habitual lenses and/or spectacles between the two visits.

3.2.4 Visit 2

1. Any changes to ocular or general health and medication will be recorded.

2. [REDACTED]

[REDACTED]

4. The Proclear MFT lenses will be applied and allowed to settle for one minute.

5. [REDACTED]

6. The subject will be allowed to adapt to the lenses away from the consulting room for 15 minutes.

7. After 15 minutes adaptation, the subject will return to the clinic.

8. [REDACTED]

9. [REDACTED]

[REDACTED]

[REDACTED]

10. [REDACTED]

[REDACTED]

11. The subject will be asked to score the following with reference to appropriate vertical visual analogue scales (0-100) [REDACTED]:

- [REDACTED]
- Distance vision
- [REDACTED]
- [REDACTED]

8. The Proclear MFT lenses will be removed.

9. The Biofinity TMF lenses will be applied and allowed to settle for one minute.

10. [REDACTED]

11. The subject will be allowed to adapt to the lenses away from the consulting room for 15 minutes.

12. [REDACTED]

[REDACTED]

[REDACTED]

[REDACTED]

15. The subject will be asked to score the following with reference to appropriate vertical visual analogue scales (0-100) [REDACTED]:

- [REDACTED]
- Distance vision
- [REDACTED]
- [REDACTED]

16. The Biofinity TMF lenses will be removed.

17. [REDACTED]

18. [REDACTED]

20. At the final visit (or when the subject is discontinued at an earlier visit) the subject will either be provided with a cash payment [REDACTED]

[REDACTED] They will then be discharged, although they may have been asked by the investigator to attend a post-study follow-up visit. They should continue to use their lenses (and solutions if applicable) as advised, and seek aftercare for their contact lenses.

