Visit 1	
Informed consent Explanation of study procedures and subject instructions Ocular, medical and contact lens histories
 
[REDACTED]
 
[REDACTED]
 
Inclusion/exclusion criteria confirmed Proclear MFT fitted (from fitting bank) 15 minutes after application:
 
[REDACTED]
 
Determination of ideal contact lens specification Proclear MFT removed and Biofinity TMF applied (from fitting bank) 15 minutes after application:
 
[REDACTED]
 
Determination of ideal contact lens specification Study lenses ordered
 
Changes to general and ocular health and medications
 
[REDACTED]
 
Proclear MFT applied 1 minute after application:
 
[REDACTED]
 
[REDACTED]
 
Lenses removed Biofinity TMF applied
 
[REDACTED]
 
[REDACTED]

Visit 2	

	Lenses removed [REDACTED]	
	Payment processed	

Table 1: Study summary.

Section 1. Overview

1.1 **Background**

This project seeks to compare the clinical performance of the Proclear Multifocal Toric and Biofinity Toric Multifocal soft contact lenses.

1.2 **Personnel**

This work will be conducted at Eurolens Research, The University of Manchester under the general direction of [name] PhD MCOptom FAAO FBCLA. The Principal Investigator for the work is [name] PhD MCOptom FAAO FBCLA.

1.3 **Study objectives**

This study aims to compare the short-term clinical performance of the two study contact lenses.

1.4 **Study design**

This will be a subject-masked, bilateral study, controlled by cross-comparison. Up to 40 subjects will wear the Proclear Multifocal Toric and the Biofinity Toric Multifocal lens in the clinic only, following an initial visit to determine ideal lens specifications.

1.5 **Statistical considerations**

The principal hypothesis to be tested in this work is that subjective scores for the lenses will be substantially equivalent. The primary outcome variable is subjective distance vision.

[REDACTED]
[REDACTED] As such, these will be compared using linear regression models or other parametric methods. [REDACTED]

[REDACTED]
[REDACTED] Deviations from this plan will be discussed in the final report. Deviations may be necessary due to differences between the actual data distribution compared with the anticipated data distribution.

1.5.1 **Missing, unused and spurious data**

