2.1.3 Inclusion criteria

Subjects will only be eligible for the study if:

1. They are aged 35 years or over and have capacity to volunteer.
2. They understand their rights as a subject and are willing to sign a Statement of Informed Consent.
3. They are willing and able to follow the protocol.
4. They agree not to participate in other clinical research for the duration of this study.
5. They are currently wearing soft contact lenses or have done so within the past 12 months.
6. They have a spherical prescription between +10.00 and -10.00DS inclusive, (based on the ocular refraction).
7. They have astigmatism of between -0.75 and -5.75DC (based on the ocular refraction) in each eye.
8. They have a reading addition component to their spectacle refraction of between +0.75 and +2.50DS.
9. They can be satisfactorily fitted with the study lenses.
10. They own a wearable pair of spectacles.

2.1.4 **Exclusion criteria**

Subjects will not be eligible to take part in the study if:

1. They have an ocular disorder which would normally contraindicate contact lens wear.
2. They have a systemic disorder which would normally contra-indicate contact lens wear.
3. They are using any topical medications such as eye drops or ointment.
4. They have had cataract surgery.
5. They have had corneal refractive surgery.
6. They have any corneal distortion resulting from previous hard or rigid lens wear or have keratoconus
7. They have any ocular abnormality which would, in the opinion of the investigator, normally contraindicate contact lens wear.
8. They have eye or health conditions including immunosuppressive or infectious diseases which would, in the opinion of the investigator, contraindicate contact lens wear or pose a risk to study personnel; or a history of anaphylaxis or severe allergic reaction.
9. They have taken part in any other contact lens or care solution clinical trial or research, within two weeks prior to starting this study.

2.2 **Subject discontinuation**

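### Does confirming eligibility before any study lens is worn let satisfactory fit (criterion 9) be decided after the primary score?

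*Combined protocol and SAP*

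**What the plan says.** - **Criterion.** Section 2.1.3, inclusion criterion 9: "They can be satisfactorily fitted with the study lenses". The visible text gives no definition of satisfactory fit and no time point.
- **Confirmation.** Section 3.2.3, step 6: "The investigator will confirm that the subject satisfies all the inclusion and exclusion criteria". Table 1 has the same order: "Inclusion/exclusion criteria confirmed Proclear MFT fitted (from fitting bank").
- **Trial fitting.** Steps 7 and 10 use the fitting set, and in each "The closest available lens specification to the subject's prescription will be selected". Step 15 then reads "The study lenses will be ordered, taking into account the manufacturers fitting guide". Table 1 lists determination of the ideal specification after each trial fitting and before ordering. Section 3.1 gives Visit 1 the task of determining specifications and Visit 2 that of assessing the lenses.
- **Replacement.** Section 2.2: "Subjects who fail to satisfy all the inclusion and exclusion criteria will be discontinued and replaced". No time limit is attached. Section 2.1.1 names, as usually replaced, those who consented but did not complete the initial visit.
- **Data.** Section 2.1.1: "All subject data will be included in the final analyses unless there are strong grounds for exclusion", with the grounds to be given in the final report. Section 1.5.1 requires unused data to be detailed and discussed, and allows partial datasets.
- **Masking.** Section 2.7: "Subjects will be masked to the two lens types by means of the investigator opening the lens packaging". The investigator is not masked in the visible text.

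**The concern.** Fit with a lens cannot be observed before the lens is worn, so step 6 asks the investigator to confirm something not yet fully known. The ordered lenses, as opposed to the fitting-set lenses, are first worn at Visit 2, in the session that collects the primary outcome. In the visible sequence the Proclear score is taken before the Biofinity lens is applied. Read alone, section 2.2 would let an investigator who knows the lens, and perhaps a score, declare a subject ineligible at that stage.

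If such rulings fell mainly on subjects with large between-lens differences, and their scores were then left out, the mean difference would shrink. Because the principal hypothesis is equivalence, that error would favour the study's own claim.

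**Working it through.** **1. Inputs (section 1.5.2).** SDs on the 0-100 scale: comfort 18, distance vision 16, near vision 19, overall 17. Meaningful difference 10, alpha 0.05, power at least 0.80, 30 completers, up to 40 recruited.

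**2. The plan's sample size.** Take a paired equivalence test (two one-sided tests), a true difference of 0, alpha 0.05 per side, and the quoted SD as the SD of the within-subject difference:

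n = [SD × (z0.95 + z0.90) / 10]² = [SD × (1.645 + 1.282) / 10]²

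| Score | SD | n (normal approximation) | Exact power at n = 30 |
|---|---|---|---|
| Comfort | 18 | 28 | 0.815 |
| Distance vision (primary) | 16 | 22 | 0.910 |
| Near vision | 19 | 31 | 0.758 |
| Overall | 17 | 25 | 0.866 |

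The stated 30 is reproduced to within one subject. The timing of criterion 9 does not enter this calculation.

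**3. What deleting scores would do.** Simulation with 400,000 trials per cell: draw 30 + k paired differences from N(10, SD), delete k, and conclude equivalence if the 90% t interval on the remaining 30 lies within -10 to +10. The correct rate is 5%.

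| Deleted | SD | At random | From the top quarter | The largest |
|---|---|---|---|---|
| k = 1 | 16 | 5.0% | 8.0% | 11.5% |
| k = 2 | 16 | 5.0% | 11.8% | 20.1% |
| k = 1 | 22.6 | 4.9% | 7.7% | 11.4% |
| k = 2 | 22.6 | 4.9% | 11.5% | 19.7% |

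The SD of 22.6 is 16 × √2, for the reading in which 16 is the SD of a single score. Among 31 subjects a quarter can be 7 or 8 people; taking 8 lowers the 8.0% to about 7.7%.

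**4. What the plan's default does.** If the k replaced subjects stay in the analysis, as section 2.1.1 provides, all 30 + k differences are used and nothing has been selected. The same simulation at SD 16 gives 5.0% for n = 31 and 5.0% for n = 32. The inflation in step 3 comes wholly from deletion, not from replacement.

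**5. Whether late fit failures are likely.** Table 2 gives one base curve and one diameter per brand (8.8 mm and 14.4 mm; 8.7 mm and 14.5 mm). The Visit 1 trial lens therefore already has the geometry of the ordered lens, and the two should differ mainly in power or axis. A mechanical fit failure first seen at Visit 2 should be uncommon. The documents give no rate: the allowance of 40 - 30 = 10 subjects covers ineligibility and discontinuation of every kind.

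**6. Timing, passages side by side.** Step 6 limits its consequence to those failing at that point. Section 2.1.1 names for replacement those who have not finished Visit 1. Table 1 and section 3.1 settle specification and ordering at Visit 1. None of these forbids a later ruling, but all point to fit being settled before ordering. Steps 8, 11, 13 and 14 and the end of step 15, where a fit confirmation would naturally sit, are blacked out and cannot be counted as absent.

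**The case for a change.** The strongest case is that steps 6 and 7 are both visible, so nothing blacked out can repair their order, and that section 2.2 stays undated whatever the hidden steps contain. Strong grounds are undefined, so a fit failure at Visit 2 might be treated as one. Explaining an exclusion in the report discloses the choice but does not fix it in advance, and the person choosing is unmasked.

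The order of the steps, the undated sentence and the undefined term all stand. Three things limit what follows:

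- A biased result needs a chain of events: a fit failure first found at Visit 2, a ruling after the score, the score dropped against the default, and removals concentrated on the lens that scored worse. The documents show none of these happening.
- The worst-case rows require deleting the largest of 31 or 32 differences. An investigator judging fit one subject at a time cannot know which difference that will be.
- Step 6 can be read as a provisional judgement. Criterion 9 asks whether the subject can be fitted, and the sphere and cylinder limits in section 2.1.3 match the lens ranges in Table 2.

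A subject who scores the first lens but cannot wear the second has no difference to retain. That is ordinary missing data, which section 1.5.1 covers, and dating criterion 9 would not supply the missing score.

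**Conclusion.** The concern does not call for a change. The wording is loose: step 6 and Table 1 confirm all criteria one step too early for criterion 9, and no visible sentence says when that criterion is finally decided. Followed as written, with scores kept by default and any exclusion justified in the report, the equivalence test keeps its 5% error rate and the target of 30 completers is unaffected.

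The 8.0% to 20.1% figures at SD 16 are conditional on selective deletion and do not describe the plan. This conclusion assumes that analysts apply the default in section 2.1.1 and do not treat a poor Visit 2 fit as sufficient reason to discard a score already given. That is the sensible reading, and a departure from it would have to appear in the final report. Whether a subject stops wearing a lens is a separate clinical matter on which nothing is said here.
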